1.4.2 Nodal Index Lesions

A nodal mass may be selected as a nodal index lesion if it is both abnormal and measurable at baseline. A lymph node lesion is considered abnormal if it has a single diameter that is > 1.0 cm and is considered measurable if it has 2 perpendicular diameters that can be accurately measured in cross section with the LD being ≥ 1.0 cm and the LPD also being ≥ 1.0 cm.

Abnormal, measurable nodal lesions will be subcategorized as either large or small.

- Large nodal lesions have an LD that is > 1.5 cm and an LPD that is ≥ 1.0 cm.
- Small nodal lesions have an LD that is > 1.0 cm and ≤ 1.5 cm and an LPD that is > 1.0 cm.

Index lesions measuring > 1.5 cm in the LD, regardless of the measurement of the LPD, will be prioritized during baseline index lesion selection.

At follow-up timepoints, the PPDs for individual nodal lesions and the SPD of all nodal index lesions will be considered. Because nodal index lesions that have one or both diameters > 0 cm and < 1.0 cm cannot be reliably measured, a default value of 1.0 cm will be assigned for each diameter that meets these criteria and the resulting PPD will be used in SPD calculations. Based on this convention, a CR may be achieved even if an SPD value is > 0 cm² (i.e., if all lymph nodes measure < 1.0 cm²).

New or enlarging nodal lesions that are still ≤ 1.0 cm by ≤ 1.0 cm will not be considered to represent recurrent or PD. A new node that measures > 1.5 cm in any diameter or a new node that measures > 1.0 cm to ≤ 1.5 cm in the LD and measures > 1.0 cm in the LPD will be considered PD.

In cases in which a large lymph node mass has split into multiple components, only those elements that are > 1.0 cm in ≥ 1 diameter will be considered abnormal and used in calculating the SPD. Components that are ≤ 1.0 cm in the LD are assumed to be normal lymph node structures. PD will not be based on the growth of a lesion sub-component until it meets the criteria for abnormal. Lesion sub-components that are abnormal (> 1.0 cm in ≥ 1 diameter) will have the true PPDs calculated with the result used only for calculating an accurate nadir. Lesion subcomponents that are normal (≤ 1.0 cm in the LD) will have the default PPD of 1.0 cm 2 (1.0 cm x 1.0 cm) stored only for the purposes of calculating the nadir value.

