1.5.2 Partial Response

To satisfy criteria for PR, all of the following conditions must be attained:

- No evidence of new disease
- $A \ge 50\%$ decrease from baseline in the SPD of the index nodal and extranodal lesions
- No increase from the nadir in the size of non-index disease
- No increase from the nadir in the size of the liver or spleen and no new liver or spleen enlargement
- If PET performed:
 - Typically FDG-avid lymphoma: if no baseline PET scan or if the PET scan was positive before therapy, the on-treatment PET is positive in ≥ 1 previously involved site—i.e., score of 4 (uptake moderately > liver) or score of 5 (uptake markedly > liver) on the Deauville 5-point scale but with reduced uptake compared with baseline. If baseline PET was performed and was negative, there is no new PET evidence of disease.
 - Variably FDG-avid lymphoma/FDG-avidity unknown: if no pretreatment PET scan or if the pretreatment PET scan was negative for lymphoma, CT criteria should be used in assessing the tumor during treatment. If the PET scan was positive before therapy, the on-treatment PET is positive in ≥ 1 previously involved site.

Version 9, 18 Feb 2020

• Persistence of bone marrow involvement in a subject who meets other criteria for CR based on the disappearance of all nodal and extranodal masses

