In cases in which a large lymph node mass has split into multiple components, only those elements that are > 1.0 cm in ≥ 1 diameter will be considered abnormal and used in calculating the SPD. Progression of the lesion can only be based on the SPD of abnormal sub-components. Lesion sub-components that are considered normal but measurable will have the true PPDs calculated, with the result used only for calculating an accurate nadir. Similarly, lesion sub-components that are visible but neither abnormal nor measurable will have the default PPD of 1.0 cm 2 (1.0 cm \times 1.0 cm) stored only for the purposes of calculating the nadir SPD value.

If lesions merge, a boundary between the lesions will be established so the LD of each individual lesion can continue to be measured. If the lesions have merged in a way that they can no longer be separated by this boundary, the newly merged lesion will be measured bidimensionally.

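### After a nodal mass splits, the rule for abnormal fragments contradicts itself, and normal fragments enter the nadir but not the SPD compared with it, which may delay SPD-based progression, mainly in CLL/SLL

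*Combined protocol and SAP*

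**What the plan says.** The text is the replacement for Appendix 2 given in the protocol's amendment history.

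**Lymphoma, section 1.4.2.** Once a large mass has split, only fragments above 1.0 cm in at least one diameter "will be considered abnormal and used in calculating the SPD". Fragments at or below 1.0 cm "are assumed to be normal lymph node structures". The same paragraph then says that the abnormal fragments "will have the true PPDs calculated with the result used only for calculating an accurate nadir". Normal fragments receive a default PPD of 1.0 cm², "stored only for the purposes of calculating the nadir value". On progression it adds: "PD will not be based on the growth of a lesion sub-component until it meets the criteria for abnormal".

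**CLL/SLL, section 2.4.1.** The opening rule is the same, but the restriction falls on the other group: "Lesion sub-components that are considered normal but measurable will have the true PPDs calculated, with the result used only for calculating an accurate nadir". Fragments that are visible but neither abnormal nor measurable are stored at 1.0 cm², and here the text names the nadir SPD as the quantity concerned. It also says that progression of a split lesion rests on the SPD of the abnormal fragments alone.

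**Nadir.** Sections 1.5 and 2.5 take the lowest recorded measurement as the reference for progression.

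**The concern.** There are two separate problems.

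First, an abnormal fragment cannot both count in the SPD and be used for nothing but the nadir. A reader or programmer who followed the later sentence of 1.4.2 would drop residual disease above 1.0 cm from the SPD and could record a response that did not occur. Section 14.1.2 makes single responses matter: in a six-subject cohort, 0/6 responders is what excludes an ORR of 35% or more.

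Second, SPD-based progression is a ratio of the current SPD to the nadir. If normal fragments sit in the nadir and not in the current SPD, the two sides measure different tissue. The stored nadir can then exceed the SPD recorded at the same visit, which conflicts with a nadir defined as the lowest recorded value. The progression threshold rises, and duration of response could lengthen.

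**Working it through.** The plan gives no figure of its own here. All lesion sizes below are assumptions chosen to illustrate.

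**Inputs**
- PR: at least a 50% "decrease from baseline in the SPD of the index nodal and extranodal lesions" (1.5.2).
- SPD-based PD: SPD at least 1.5 × nadir SPD (1.5.4, 2.5.4).
- Single-node PPD rule, lymphoma (1.5.4): PPD up at least 50%, LD above 1.5 cm, a change of at least 0.5 cm in LD or LPD, and a dimension of at least 2.0 cm.
- Single-node rule, CLL/SLL (2.5.4): LD up at least 50%, with LD at least 1.5 cm and LPD at least 1.0 cm.
- Stored normal fragment: 1.0 cm² each. Section 2.4.1 keeps the true PPD when the fragment is measurable; I take 1.0 cm² throughout.

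**Step 1: abnormal fragments, lymphoma.** A 4.0 × 4.0 cm mass (16.0 cm²) splits into 2.5 × 2.5 = 6.25 and 2.0 × 1.8 = 3.60 cm².
- Counted in the SPD: 6.25 + 3.60 = 9.85; decrease 1 − 9.85/16.0 = 38%, so no PR.
- Nadir only: SPD 0, decrease 100%, so the SPD criterion for PR is met.

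**Step 2: normal fragments and the PD threshold.** Let A be the abnormal-fragment SPD at nadir, A′ the later value and k the number of normal fragments.
- Mismatch (nadir A + k, current A′): PD when A′ ≥ 1.5(A + k), a rise of 50% + 150% × k/A.
- Counted on both sides: A′ + k ≥ 1.5(A + k), so A′ ≥ 1.5A + 0.5k.
- Counted on neither side: A′ ≥ 1.5A.

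| A (cm²) | k | Mismatch | Both sides | Neither side |
|---|---|---|---|---|
| 5.5 | 1 | 9.75 (+77%) | 8.75 (+59%) | 8.25 (+50%) |
| 5.5 | 3 | 12.75 (+132%) | 9.75 (+77%) | 8.25 (+50%) |
| 20 | 1 | 31.5 (+57.5%) | 30.5 (+52.5%) | 30.0 (+50%) |

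In the first row the stored nadir is 5.5 + 1.0 = 6.5 cm², while the SPD recorded at that visit is 5.5 cm².

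**Step 3: lymphoma, what the single-node PPD rule catches.** If the abnormal-fragment SPD has risen by 50%, at least one fragment's PPD has risen by 50% or more. The rule therefore fires unless the absolute-size conditions fail.
- Caught: 1.8 × 1.5 = 2.70 cm² growing to 2.3 × 1.92 = 4.42 cm² (+64%), with LD up 0.5 cm to 2.3 cm.
- Not caught: 2.70 cm² growing to 2.2 × 1.9 = 4.18 cm² (+55%), because each diameter changes by only 0.4 cm. With one normal fragment present, counting it on neither side gives PD (4.18 against 4.05). The mismatch does not (4.18 against 1.5 × 3.70 = 5.55), nor does counting it on both sides (5.18 against 5.55). One convention therefore has to be chosen.
- Illustrative simulation (200,000 draws; 1 to 4 abnormal fragments of about 1 to 4 cm, 1 to 3 normal fragments): in 27,848 cases the mismatch withheld an SPD-based PD that counting on both sides would have called. All but 612 (612/27,848 = 2.2%) met the single-node PPD rule. This assumes that a fragment counts as an individual node.

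**Step 4: CLL/SLL, what the single-node rule catches.** With proportional growth, a 50% rise in LD is a PPD factor of 1.5² = 2.25, or +125%. For one fragment with A = 5.5 and k = 1, the LD rule fires at 5.5 × 2.25 = 12.38 cm², beyond the mismatched SPD threshold of 9.75. Between 8.25 cm² (8.75 if counted on both sides) and 9.75 cm², neither rule calls PD. The LD rule takes over only when 50% + 150% × k/A exceeds 125%, that is when k/A is above 0.5. The k = 3 row is such a case (12.38 against 12.75).

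**The case against.** The strongest reply is that context settles the first problem. Section 1.4.2 says outright that abnormal fragments enter the SPD, 2.4.1 bases progression on their SPD, and the misplaced restriction looks like a swapped word. That stands: the 100% decrease in Step 1 shows what the literal wording permits, not what the plan intends. The contradiction still has to be removed.

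On the second problem, 1.4.2 says only a nadir value, and 1.4.1 defines nadirs both for individual lesions and for the sum. The stored 1.0 cm² could be a fragment's own reference in case it grows, which fits the neighbouring sentence on fragment growth. That stands for lymphoma, where the mismatch is a possible reading. It fails for CLL/SLL, where 2.4.1 names the nadir SPD. The single-node PPD rule also answers most of the lymphoma cases, but the CLL/SLL rule does not do the same work.

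A reader might infer that storing normal fragments in the nadir overstates shrinkage. It cannot, because PR is measured from baseline. A reader might also object that these fragments are left out of the SPD at all, since for an unsplit node below 1.0 cm "the resulting PPD will be used in SPD calculations". On a 12.0 cm² baseline one fragment is worth 1.0/12.0 = 8.3 percentage points. But treating fragments of 1.0 cm or less as normal tissue is a stated choice, not an error.

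Two limits on size also stand. The documents give no frequency of split masses. And the expansion cohorts in Table 2 of section 6.1.2, as amended, are FL, MZL and DLBCL, so the CLL/SLL effect falls on dose-escalation subjects.

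**Conclusion.** The point holds in two parts. Section 1.4.2 contradicts itself on abnormal fragments; this does harm only if the nadir-only sentence is applied. The handling of normal fragments gives a mismatched SPD-to-nadir comparison, explicit in 2.4.1 and possible in 1.4.2. The excess rise required is 150% × k/A: 27 percentage points at A = 5.5 cm² and k = 1, and 7.5 at A = 20 cm². It is material for small residual disease and minor for large. SPD-based progression may be delayed, mainly in CLL/SLL. Other routes to PD (single node, new lesion, non-index disease, organ enlargement) remain open, so delay is not general.

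A reader might go further and conclude that both problems favour the drug, or that PFS is lengthened. The documents do not support that. The first causes no bias on the reading the rest of the text points to. Sections 14.3.1 and 14.3.2, as amended, speak of time-to-event outcomes generally and of time to response and duration of response; they do not name PFS.

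The verdict rests on assumed lesion sizes and on this wording still being in force. The current Appendix 2 was not available to this review; the later amendment entries available show no change to it.

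**What to change.** First confirm the wording in the current Appendix 2. Then:

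- In 1.4.2, state that the true PPDs of abnormal fragments count in both the SPD and the nadir, and reconcile the sentence with 2.4.1.
- In 1.4.2 and 2.4.1, require the same set of fragments on both sides of every SPD-to-nadir comparison. Any PPD stored for a normal fragment serves only as that fragment's own reference if it later becomes abnormal.

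The cost is two sentences, one programming check, and recalculation for subjects whose masses split. I see no real downside.

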1.4.3 Extranodal Index Lesions

An extranodal mass may be selected as an index lesion if it is both abnormal and measurable at baseline. An extranodal mass of any size is considered abnormal. It is considered measurable at baseline if it has 2 perpendicular diameters that can be

Version 9, 18 Feb 2020

accurately measured in cross section with the LD being \geq 1.0 cm and the LPD also being \geq 1.0 cm.

At follow-up timepoints, the PPD of each single extranodal index lesion and the SPD of all extranodal index lesions will be considered. Because extranodal index lesions that have one or both diameters < 0.5 cm and > 0 cm cannot be reliably measured, a default value of 0.5 cm will be assigned for each diameter that meets these criteria and the resulting PPD will be used in SPD calculations. If an extranodal lesion is no longer clearly visible, it will be considered resolved and its PPD will be defined as 0 cm^2 .

If an extranodal lesion that had resolved (i.e., had a PPD of 0 cm²) subsequently reappears, the subject will be considered to have PD. A new extranodal lesion of any size that appears at a site that was not previously involved with lymphoma and is discernible to the radiologist by CT scan will be considered PD.

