1.5.4 Progressive Disease

The occurrence of any of the following events indicates progressive disease (PD):

- Evidence of any new disease that was not present at baseline:
 - A new node that measures > 1.5 cm in any diameter
 - A new node that measures > 1.0 cm to ≤ 1.5 cm in the LD and > 1.0 cm in the LPD
 - Reappearance of an extranodal lesion that had resolved (i.e., had previously been assigned a PPD of 0 cm²)
 - o A new extranodal lesion of any size
 - New non-index disease (e.g., effusions, ascites, or other organ abnormalities) of any size unequivocally attributable to lymphoma (usually requires PET, biopsy, cytology, or other non-radiologic confirmation to confirm disease attributable to lymphoma). Note: Isolated new effusions, ascites, or bone lesions are not sufficient evidence alone of PD unless histologically confirmed. In patients with no prior history of pulmonary lymphoma, new lung nodules identified by CT are usually benign. Thus, a declaration of PD should not be made if this is the only manifestation of an apparently new lesion.
 - New FDG-avid foci consistent with lymphoma rather than another etiology (e.g., infection, inflammation). If there is uncertainty regarding the etiology of new lesions, biopsy or interval scan may be considered.
 - New or recurrent bone marrow involvement with lymphoma by PET-CT or by bone marrow biopsy if prior PET-CT or bone marrow biopsy performed as part of the study was negative for lymphoma.
- Evidence of worsening of nodal or extranodal index lesions:
 - Increase from the nadir by \geq 50% in the SPD of index lesions
 - Evidence of worsening of individual index lymph nodes or nodal masses:
 - Increase from the nadir by ≥ 50% in the PPD for any individual node if the node now has an LD of > 1.5 cm and there is an absolute change from the nadir of ≥ 0.5 cm in the LD or LPD and to an absolute dimension of ≥ 2.0 cm.

Version 9, 18 Feb 2020

- Increase from the nadir by ≥ 50% in the LD for any individual node if the node now has an LD of > 1.5 cm and there is an absolute change from the nadir of > 0.5 cm in the LD
- Increase from the nadir by ≥ 50% in the LPD for any individual node if the node now has an LPD of > 1.5 cm and there is an absolute change from the nadir of ≥ 0.5 cm in the LPD
- If a lesion had been classified as a small lymph node, there is an additional requirement that the lesion has an LD of > 1.0 cm and an LPD of > 1.0 cm
- Unequivocal increase in the size of non-index disease

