6.8.3.4. Rituximab Dose Modifications and Supportive Care

Rituximab-related noninfectious pneumonitis has been described (Subramanian 2010) with an incidence of ~4.3% (Salmasi 2010). In patients developing rituximab-associated pneumonitis, the mean time from the first rituximab infusion to the onset of respiratory symptoms was 3 months, with a peak incidence after administration of a mean cumulative dosage of 1600 mg/m2 (Lioté 2010).

Severe, including fatal, mucocutaneous reactions can occur in patients receiving rituximab during infusion or at later timepoints. Non-infusion related events have included paraneoplastic pemphigus, Stevens Johnson syndrome, lichenoid dermatitis, vesiculobullous dermatitis, and toxic epidermal necrolysis (Genentech 2016). The onset of these reactions has varied from 1 to 13 weeks following initiation of rituximab exposure.

Among patients receiving rituximab in combination with chemotherapy, rare instances of life-threatening bowel obstruction or perforation has been observed [Ram 2009], primarily in patients with NHL. In post-marketing reports, the mean time to documented gastrointestinal perforation was 6 (range 1–77) days from start of chemoimmunotherapy.

Fulminate and fatal HBV infection and reactivation can occur during or after treatment with rituximab (Genentech 2016). The risk is very low among patients with negative anti-HBc serology (Matsue 2010) and/or undetectable HBV DNA as assessed by quantitative PCR. Because subjects with such evidence of persistent HBV infection are excluded from this study, reactivation is not anticipated. Other serious bacterial, fungal, and new or reactivated viral infections have also occurred during and for ~1 year following rituximab-based therapy (Gea-Banacloche 2010). Other new or reactivated viral infections in patients receiving rituximab have included CMV, herpes simplex virus, parvovirus B19, varicella zoster virus, West Nile virus, and HCV. Progressive multifocal leukoencephalopathy (PML) due to polyomavirus JC has been observed in patients who have received rituximab therapy for hematologic malignancies (Carson 2009).

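### Lymphoma response criteria: an isolated new lung nodule is PD under 1.4.3 and a 1.5.4 bullet, but not PD under the 1.5.4 note, and no precedence is stated

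*Combined protocol and SAP*

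**What the plan says.** The text is in the lymphoma part of Appendix 2, shown in the amendment history just before the changes of Amendment 4 (07 Nov 2016).

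- **1.4.3 Extranodal Index Lesions.** "A new extranodal lesion of any size that appears at a site that was not previously involved with lymphoma" counts as PD once a CT scan shows it. The only conditions are an uninvolved site and visibility.
- **1.5.4 Progressive Disease, extranodal bullet.** Any one listed event is enough for PD, and one of them is "A new extranodal lesion of any size", with no further condition.
- **1.5.4, bullet on new non-index disease.** This one does carry a condition: the finding must be unequivocally attributable to lymphoma, usually with non-radiologic confirmation.
- **1.5.4, note in the same list.** "Isolated new effusions, ascites, or bone lesions are not sufficient evidence alone of PD unless histologically confirmed". It continues: "In patients with no prior history of pulmonary lymphoma, new lung nodules identified by CT are usually benign", and PD should then not be declared if nothing else is new.
- **1.4.4 Non-Index Lesions.** Bone lesions, and extranodal lesions with both diameters under 1.0 cm, may be treated as non-index disease.
- **1.5 and 1.5.1 to 1.5.3.** Best overall response is counted only until PD, and CR, PR and SD each require that there be no new disease.

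**The concern.** Two lines score a new extranodal lesion as PD whatever its cause. A third line tells the reader not to do so for a finding that meets those two lines exactly. Two assessors who both follow the text could score the same scan differently, and the one who applies 1.4.3 literally would record as progression something the plan itself describes as usually benign.

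The endpoint at stake is objective response rate (ORR). Because response is counted only until PD, a subject who is scored PD on a benign nodule and would have responded later is lost as a responder. Section 14.1.2 judges the two FL regimens by responder counts in up to about 20 evaluable subjects each, so a single subject can matter.

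**Working it through.** The main check is textual.

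| Isolated new finding on CT | 1.4.3 | 1.5.4 extranodal bullet | 1.5.4 non-index bullet | 1.5.4 note |
|---|---|---|---|---|
| Lung nodule, no prior pulmonary lymphoma | PD | PD | PD only if attributable to lymphoma | Not PD |
| Bone lesion, no histology | PD if read as an extranodal lesion | PD if read as an extranodal lesion | PD only if attributable to lymphoma | Not PD |
| Lung nodule, prior pulmonary lymphoma | Not covered if the lung counts as a previously involved site | PD | PD only if attributable to lymphoma | Silent |

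1. *First row.* The note's restriction to patients without prior pulmonary lymphoma is the uninvolved-site situation of 1.4.3, so the rules meet head on. Section 1.4.3 does not refer to the note, and neither section says which line prevails.
2. *Second row.* Section 1.4.4 lets a bone lesion be non-index disease. Attribution is then already required, and the note agrees with the bullet. A conflict arises only if the lesion is read as extranodal under 1.4.3.
3. *Third row.* The note does not apply, so it creates no contradiction.

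The plan states no figure for this rule, so there is none to reproduce. To show what one subject can do, I took the FL boundaries of 14.1.2 at N = 20.

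- Inputs: monotherapy boundary 8/20 against an ORR of 20%; LAM-002A/rituximab boundary 12/20 against 39%.
- Lower one-sided 95% bound (Clopper-Pearson) for r responders in n: the 0.05 quantile of a Beta(r, n − r + 1) distribution.
- Exact one-sided p: P(X ≥ r) for X ~ Binomial(n, p0).

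| Regimen | r/n | Lower 95% bound | p0 | Exact p | Boundary met |
|---|---|---|---|---|---|
| Monotherapy | 8/20 | 21.7% | 20% | 0.032 | Yes |
| Monotherapy | 7/20 | 17.7% | 20% | 0.087 | No |
| With rituximab | 12/20 | 39.4% | 39% | 0.047 | Yes |
| With rituximab | 11/20 | 34.7% | 39% | 0.109 | No |

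The 8/20 and 12/20 rows agree with the plan's statement that its boundary values keep the lower bound at or above 20% and 39%. Removing one responder reverses the conclusion in each regimen.

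**The case against.** *The note may be a specific exception to a general rule.* All of these lines sit in one list on new disease, and the note speaks of an apparently new lesion without limiting itself to non-index disease. That is a sensible reading and probably the intended one. But the text does not say so, and 1.4.3 stands in a separate section with no pointer to the note. I put no weight on how the bullets are indented, since that may come from the PDF conversion.

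*The plan has safeguards.* The closing note of 1.5.4 and section 6.12 allow treatment to continue under observation when true progression is uncertain, and 6.12 says subjects may be withdrawn, not that they must be. A reader might infer that a nodule automatically ends therapy; the documents do not support that. The safeguards do not, however, say which line governs scoring.

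*Few subjects are exposed.* A response already recorded is not erased by a later PD. The first on-study scan comes within 7 days before Cycle 3 Day 1, so only subjects who have not yet responded by the time of the false PD can be lost to ORR. This stands.

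*The operative appendix is not in the part shown.* This also stands. But both sides of the conflict are in the same inserted text, so it is not a difference between a change log and current wording, and no later amendment visible here lists a change to these criteria.

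**Conclusion.** The contradiction is real for isolated new lung nodules in patients with no prior pulmonary lymphoma, and weaker for bone lesions. As written, the rule can produce a PD that the plan itself says should not be declared. One subject reclassified this way can decide an FL boundary at N = 20, in either regimen. The conclusion assumes that the current Appendix 2 keeps the inserted wording.

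Three stronger readings are not supported.

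- *A rate of false PD.* Section 6.8.3.4 says "Rituximab-related noninfectious pneumonitis has been described", with an incidence of about 4.3%, and a reader might turn that into an expected number of false progressions. It would count pneumonitis cases only. No section says that pneumonitis appears as a discrete new lesion, and the reference list describes the source as a study of patients on immunochemotherapy, which these cohorts do not receive. The frequency cannot be derived.
- *Drug-related findings scored as PD, mainly in the combination cohorts.* This is inference. The note says only that such nodules are usually benign.
- *Shortened progression-free survival.* The visible text refers to time-to-event outcomes without defining this one, so I rest the point on best response alone.

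**What to change.** Reconcile 1.4.3 and 1.5.4 for endpoint scoring:

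1. In 1.4.3 and in the 1.5.4 extranodal bullet, add the condition that the new lesion be unequivocally attributable to lymphoma, as 1.5.4 already requires for new non-index disease.
2. State that the 1.5.4 note on lung nodules, effusions, ascites and bone lesions applies to the extranodal bullet and to 1.4.3 as well as to non-index disease.
3. Check the wording against the current Appendix 2 before editing.

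This is one clause in two places and one sentence of scope. The downside is that a few PD calls will wait for a later scan. If progression is then confirmed, the closing note of 1.5.4 already dates it to the first objective documentation. The change concerns scoring only and does not touch the decision to continue treatment.
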